# 6. Other analyses, data summaries, and graphs

## Other data summaries

Data on the clinical management of patients during intervention period will be summarised for each treatment group by the mean and standard deviation or median and interquartile range for continuous variables, and the number and percent for categorical variables.

The individual components of each composite outcome (postoperative infection with 30 days of randomisation, acute cardiac event within 24 hours of randomisation, and acute cardiac event

<sup>b Based on OPTIMISE I

within 30 days of randomisation) will be summarised by treatment arm using the number and percent.

Follow up data collected which is not for primary, secondary or process outcomes will be summarised by treatment group by the mean and standard deviation or median and interquartile range for continuous variables, and the number and percent for categorical variables. Differences between groups will not be presented and no statistical tests will be performed on this data.

For details of summaries see draft tables in appendix 5.

#### **Protocol Deviations**

The number and percent of patients with at least one protocol deviation will be summarised for each treatment arm. In addition, in the intervention group this we will provide summaries of the number of patients who did not receive cardiac output monitoring and the number of patients who did not received the wrong dose. For the usual care group we will summarise the number of patients who received cardiac output monitoring.

#### Safety analyses

We will report the total number and percent of serious adverse events (SAEs) related to the OPTIMISE II intervention in each treatment group and the number of patients with at least one SAE by treatment group.

#### Graphs

We will present a Kaplan-Meier plot displaying the survival curve for each treatment arm for postoperative infection within 30 days of randomisation.

We will display the cumulative incidence for postoperative infection up to 30 days of randomisation, taking into account death as a competing risk, based on the competing risks model described in the sensitivity analysis above.

We will display the survival curve for each treatment arm for mortality up to 180 days from randomisation using a Kaplan-Meier plot.

We will display the results of the sensitivity analysis for missing data being MNAR in a graph showing the different treatment estimates and 95% CIs obtained under different assumptions about the event rate in those with missing data.

[figure not shown]

# 8. Appendices

## **Appendix 0: Determining primary outcome status**

Determining whether a patient has experienced one of the components of the primary outcome will be carried out by the following process:

#### **Appendix 1: Deriving outcomes**

### **Primary Outcome**

#### Postoperative infection within 30 days of randomisation

- Equal to 1 if:
  - At least one of the components of postoperative infection is Clavien-Dindo II or greater:
  - o AND Date of diagnosis of first postoperative infection is within 30 days of randomisation.
- Equal to 0 if:
  - All of the components of postoperative infection are "None" or Clavien-Dindo I or the date of diagnosis of first infection is after 30 days of randomisation.
- Missing if:
  - All components are missing
  - One or more of the components of postoperative infection is missing and all other components are "None" or Clavien-Dindo I
  - One or more of the components of postoperative infection is Clavien-Dindo II or greater and date of diagnosis of first postoperative infection is missing.

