# 4. Sample size and randomisation

#### Sample size calculation

In order to detect a 5% absolute reduction (from 30% to 25%) for the primary outcome of postoperative infection up to 30 days (a risk ratio of 0.83), with 80% power, and an overall type I error rate of 5%, we require 2502 patients (1251 per arm). This sample size would also allow us to detect an absolute reduction in the primary outcome of 6% (from 30% to 24%) with 92% power.

[figure not shown]

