#### **General analysis principles**

Analyses will follow the intention-to-treat principle: all randomised patients with a recorded outcome will be included in the analysis, and analysed according to the treatment to which they were randomised (1). Definitions of what constitutes a recorded outcome for each outcome can be found in Appendix 1. Patients with missing outcome data will be excluded from the analysis. Missing data for baseline covariates to be included in the analysis model will be accounted for using mean imputation (2).

For the analysis of the primary outcome, each secondary outcome, and all process measures, we will present the following information:

- The number of patients included in each analysis, by treatment arm
- A summary statistic of the outcome (e.g. number (%)), by treatment arm
- The estimated treatment effect
- A 95% confidence interval for the estimated treatment effect
- A two-sided p-value

For all analyses, a significance level of 5% will be used.

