#### Sensitivity and secondary analyses

#### **Missing Data**

If the level of missing data for the primary outcome exceeds 1% of randomised patients, we will perform a sensitivity analysis to assess the robustness of our analysis of the primary outcome in regard to the data being missing-not-at-random (MNAR). For example, this could occur if patients who were discharged home and had no postoperative infection were less likely to respond to their telephone follow-up after 30 days than patients who did have a postoperative infection.

We define  $\delta_0$  and  $\delta_1$  as follows:

- ullet  $\delta_0$  = assumed event rate amongst patients with missing outcome data in the control arm
- $\delta_1$  = assumed event rate amongst patients with missing outcome data in the control arm

I.e. a value of  $\delta_0$ =0.3 indicates that we would assume 30% of patients with missing outcome data in the control arm experienced an event (postoperative infection).

We will conduct sensitivity analyses using the following values of  $\delta_0$ :

• 
$$\delta_0 = 0.15, 0.2, 0.25, 0.3, 0.35, 0.4$$

For each value of  $\delta_0$ , we will use the following values of  $\delta_1$ :

$$\delta_1$$
 =  $\delta_0$  + 0.1,  $\delta_0$  + 0.05,  $\delta_0$ ,  $\delta_0$  - 0.05,  $\delta_0$  - 0.1

For example, for the scenario where  $\delta_0$ =0.2 and  $\delta_1$ = $\delta_0$  + 0.1, we will assume that 20% of patients with missing outcome data in the control arm experience an event, and 30% of patients with missing data in the intervention arm experience an event.

For each different combination of  $\delta_0$  and  $\delta_1$  we will estimate a treatment effect and 95% CI using the imputation approach outlined below. For each scenario we will perform carry out 10 imputations and combine the results to give one estimate of the treatment effect for that scenario.

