#### Acute cardiac event of Clavien-Dindo grade II or greater, within 24 hours of randomisation

Equal to 1 if:

- At least one of the components of acute cardiac event within 24 hours is Clavien-Dindo II or greater.
- Equal to 0 if:
  - All of the components of acute cardiac event within 24 hours are equal to "None" or Clavien-Dindo I
- Missing if:
  - All components are missing
  - One or more of the components of acute cardiac event within 24 is missing and all other components are "None" or Clavien-Dindo I

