#### Acute cardiac event of Clavien-Dindo grade II or greater, within 30 days of randomisation

- Equal to 1 if:
  - At least one of the components of acute cardiac event within 30 days of randomisation is Clavien-Dindo II or greater.
- Equal to 0 if:
  - All of the components of acute cardiac event within 30 days of randomisation are non-missing and equal to "None" or Clavien-Dindo I
- Missing if:
  - All components are missing
  - One or more of the components within 30 days of randomisation is missing and all other components are "None" or Clavien-Dindo I

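### A patient with a blank infection component is kept if a recorded component is an event and dropped if not, and the missing-data sensitivity grid does not separate these patients from fully missing ones (minor).

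*SAP*

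**What the plan says.** SAP Appendix 1 (Deriving outcomes, primary outcome) scores a patient 1 once any one component is grade II or greater and the first infection is dated within 30 days; the other components need not be recorded. It sets the outcome to missing if "One or more of the components of postoperative infection is missing and all other components are 'None' or Clavien-Dindo I". A recorded event with no date is also missing. A first infection dated after day 30 counts as 0.

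General analysis principles (section 5) excludes patients with a missing outcome.

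If more than 1% of randomised patients lack the primary outcome, the Missing Data section plans a missing-not-at-random analysis. Assumed control rates are "0.15, 0.2, 0.25, 0.3, 0.35, 0.4", and the intervention rate differs from control by at most 0.10 either way. The Imputation model section and the Appendix 4 code order all missing patients of an arm at random and assign events to the chosen proportion. Neither uses recorded components or the reason for missingness.

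The two cardiac composites follow the same rule: "One or more of the components of acute cardiac event within 24 is missing and all other components are 'None' or Clavien-Dindo I" at 24 hours and "One or more of the components within 30 days of randomisation is missing and all other components are 'None' or Clavien-Dindo I" at 30 days. The Missing Data section covers only the primary outcome.

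**The concern.** Two patients with the same blank field are treated differently because of what the other fields show: in general the one with an infection stays and the one without leaves. Even if blanks arise completely at random, the composite is then missing not at random, and covariate adjustment cannot repair that. The mechanism the SAP has in mind is a different one, namely whole-patient non-response to the 30-day telephone call.

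The sensitivity analysis pools three kinds of patient: nothing recorded, partly recorded with no event, and recorded event with no date. One rate per arm cannot suit all three. At stake are the reported infection percentages, the risk differences planned for the analysis of patients who undergo surgery, and the odds ratio if completeness differs by arm. The last is possible because the trial is open and Table 14 foresees assessors who know the allocation.

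**Working it through.** **Inputs from the SAP.** Rates come from Sample size calculation: "In order to detect a 5% absolute reduction (from 30% to 25%) for the primary outcome". There are 1251 patients per arm and seven components (section 3). The control grid is 0.15 to 0.40, with intervention within 0.10 of it (Missing Data).

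**Assumptions, not in the SAP.** Components are independent with equal risk; a partly recorded patient has one blank unless stated; blanks arise at random within arm; blank rates are 1% to 5%.

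**Reproducing the plan's figures.** Two-sided 5%, pooled variance, no continuity correction: n = [1.960·√(2·0.275·0.725) + 0.842·√(0.30·0.70 + 0.25·0.75)]² / 0.05² = 1250.7, so 1251 per arm and 2502 in total, as stated. The same method gives 92.3% power for the second scenario, "6% (from 30% to 24%) with 92% power". The true odds ratio is (0.25/0.75)/(0.30/0.70) = 0.778.

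**Residual risk of a dropped patient.** Per-component risk is q = 1 − (1 − p)^(1/7), or 0.0497 at p = 0.30 and 0.0403 at p = 0.25. With k blanks and all recorded components negative, the risk is 1 − (1 − q)^k.

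| Blanks | 1 | 2 | 3 | 4 | 5 | 6 |
|---|---|---|---|---|---|---|
| p = 0.30 | 5.0% | 9.7% | 14.2% | 18.4% | 22.5% | 26.3% |
| p = 0.25 | 4.0% | 7.9% | 11.6% | 15.2% | 18.6% | 21.9% |

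If equal shares are dropped, a single blank component reaches 15% only if it carries ln(0.85)/ln(0.70) = 46% of the composite's log-survival.

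**Grid.** There are 6 × 5 = 30 scenarios. Control is never below 0.15. Intervention is below 0.15 in three only: (0.15, 0.05), (0.15, 0.10) and (0.20, 0.10), written as (control, intervention). No scenario has both arms at or below 0.10.

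**Effect of the exclusion rule.** Let m be the share with one blank and e = 1 − (1 − q)^6 the chance of an event among the other six (0.2634 control, 0.2185 intervention).

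- Analysed risk = [p(1 − m) + m·e] / [(1 − m) + m·e]
- Dropped share d = m(1 − e)

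Example, 1% control and 5% intervention:

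- Control: (0.2970 + 0.0026)/(0.9900 + 0.0026) = 0.3019
- Intervention: (0.2375 + 0.0109)/(0.9500 + 0.0109) = 0.2585
- Odds ratio: (0.2585/0.7415)/(0.3019/0.6981) = 0.806

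| Blanks, control / intervention | Analysed risks (truth 30.0% / 25.0%) | Difference (truth −5.0) | OR (truth 0.778) | OR under no effect |
|---|---|---|---|---|
| 3% / 3% | 30.6% / 25.5% | −5.1 | 0.778 | 1.00 |
| 5% / 5% | 31.0% / 25.9% | −5.1 | 0.778 | 1.00 |
| 1% / 5% | 30.2% / 25.9% | −4.3 | 0.806 | 1.04 |
| 5% / 1% | 31.0% / 25.2% | −5.8 | 0.750 | 0.964 |

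**What the planned grid does with this.** After imputation at rate δ an arm's risk is analysed risk × (1 − d) + δ·d.

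- 1% / 5%: dropped shares are 0.7% and 3.9%, about 2.3% overall, so the 1% trigger is met. Point (0.15, 0.05) gives OR 0.777 and (0.15, 0.10) gives 0.785, on either side of 0.778.
- 5% / 1%, no effect: the closest of the 30 points is (0.15, 0.25), at 0.990; every other point is lower. A low pair outside the grid, (0.05, 0.05), gives 1.00. Counting the dropped patients as 0 gives 1.007.

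**The case against.** The case for leaving the plan alone has weight. One qualifying component settles a composite; without one, a blank leaves it unsettled, and calling that missing is a defensible convention. The treatment effect in Table 3 is an odds ratio, which does not move when blank rates are equal. The bias needs an imbalance that nothing in the SAP predicts, and even at 1% / 5% it is ln(0.806/0.778) = 0.035 on the log scale, about 0.4 of an unadjusted standard error (√[1/(1251·0.21) + 1/(1251·0.1875)] = 0.090). In that direction the planned grid already brackets the truth. The process in Appendix 0 for determining outcome status is not shown in the text available, and it may make partial records rare. All of this stands and limits the size of the point. It does not remove the outcome-dependent exclusion or the gap in the grid in the reverse direction.

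Stronger readings are tempting but not supported:

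- That every partly recorded patient who stays is an event. An infection dated after day 30 can be kept as 0, and a recorded event with no date is dropped.
- That the sensitivity analysis overwrites negative findings. The Appendix 4 code fills the composite only where it is missing; it ignores recorded components and does not alter them.
- That the grid is implausibly high for all these patients. With four or more blanks the residual risk lies inside it, and the intervention arm does reach 0.05, though only beside control 0.15.

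**Conclusion.** The point holds as a minor one. The derivation rule makes exclusion of partly recorded patients depend on the outcome, apart from undated events and late infections. With equal blank rates the consequence is about half a percentage point on each arm's infection rate at an assumed 3%, with no change in the odds ratio. With rates of 1% and 5% the odds ratio moves from 0.778 to 0.806 or 0.750 according to direction, and a true null to 1.04 or 0.964. A reader might infer that the primary odds ratio is biased as planned; the SAP gives no ground for that without a difference in completeness between arms.

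The sensitivity analysis fits this group poorly when one to three components are blank, because it has no scenario with low rates in both arms. These sizes rest on equal, independent components and on assumed blank rates, neither of which the SAP states. If no more than 1% of outcomes are missing, the effect is negligible.

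**What to change.** Before unblinding, amend the SAP as follows.

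1. Report missing primary outcomes by pattern and arm: all components missing, partly recorded with no event, recorded event without a date.
2. Pre-specify a sensitivity analysis of the primary outcome that counts partly recorded patients with no recorded event as 0.
3. In the missing-not-at-random analysis, apply low rates (0, 0.05, 0.10) in both arms to those patients and keep the 0.15 to 0.40 control grid for patients with all components missing.
4. Run the analysis in item 2, with blanks taken as 'None', for the two cardiac composites, which have no missing-data sensitivity analysis now.

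Model-based imputation of the blank components is optional. It is not what the planned random-ordering code does and would need new models and code. The cost of the four items is SAP wording, a small change to the Appendix 4 code, a little more analysis, and an explicit assumption for what may be a small group. Sample size and primary model stay as they are.

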#### **Secondary Outcomes**

#### Mortality within 180 days of randomisation

- Equal to 1 if:
  - o Patient status at 180 day follow up is dead
  - AND date of death is within 180 days of randomisation
- Equal to 0 If:
  - o Patient status at 180 day follow up is alive
  - Missing if: Patient status at 180 day follow up is missing
  - o OR patient status at 180 day follow up is dead and date of death is missing

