#### Discharge event

- Patients will be classified as discharged if patient survived to discharge for primary hospital admission.
- Patient will be classified as died before discharge if patient did not survive to discharge for primary hospital admission.
- Discharge event will be missing if item "Did the patient survive to discharge from primary hospital admission?" is missing.

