#### Number of critical care free days up to 30 days from randomisation

- If patient is alive 30 days from randomisation:
  - equal to 30 (total duration of level 2 critical stay within 30 days of randomisation + total duration of level 3 critical stay within 30 days of randomisation)
- If patient died within 30 days of randomisation
  - equal to (date of death date of randomisation) (total duration of level 2 critical stay within 30 days of randomisation + total duration of level 3 critical stay within 30 days of randomisation).
- Missing if:
  - o Total duration of level 2 critical stay within 30 days of randomisation is missing
  - o OR total duration of level 3 critical stay within 30 days of randomisation is missing
  - o Or Mortality at 30 days is missing

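### Appendix 1 codes a recorded death as missing when the 180-day status is blank, gives deaths after day 180 no class, and sends undated grade II+ infections into an unsuitable imputation grid

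*SAP*

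**What the plan says.** In Appendix 1, mortality within 180 days equals 1 when "Patient status at 180 day follow up is dead" "AND date of death is within 180 days of randomisation". It equals 0 when "Patient status at 180 day follow up is alive". The rule for missing is "Missing if: Patient status at 180 day follow up is missing", "OR patient status at 180 day follow up is dead and date of death is missing".

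Other derivations in Appendix 1 use further information on death. The discharge event rests on the item "Did the patient survive to discharge from primary hospital admission". Critical care free days uses the date of death and has the condition "Or Mortality at 30 days is missing".

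For the primary outcome, one of the conditions for missing is: "One or more of the components of postoperative infection is Clavien-Dindo II or greater and date of diagnosis of first postoperative infection is missing". A first infection dated after day 30 is explicitly coded 0.

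General analysis principles (Section 5) excludes patients with missing outcomes. The missing-not-at-random (MNAR) analysis in Section 5 covers the primary outcome only and runs only if more than 1% of randomised patients lack it. Its code in Appendix 4 imputes every patient whose infection outcome is missing, for whatever reason.

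**The concern.** Death cannot be undone. A patient recorded as having died in hospital has a known 180-day outcome whether or not a later status field was completed. As written, the rule discards that outcome, and no sensitivity analysis for mortality would recover it. The gap for deaths after day 180 leaves a decision to the programmer once data are in hand.

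For infection, the patient most likely to be a true event among those coded missing is the one with a recorded grade II+ infection and no date. The MNAR analysis treats that patient like one about whom nothing is known. At stake are the counted deaths and infections and, if completeness differs between the arms of this open trial, the odds ratios.

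**Working it through.** **1. Running the written rules over the possible records.**

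| 180-day status | Date of death | Class under Appendix 1 |
|---|---|---|
| dead | day 20 or day 180 | 1 |
| dead | day 190 | none of the three |
| dead | missing | missing |
| alive | – | 0 |
| blank | none known | missing |
| blank | day 20 or day 180, recorded elsewhere | missing |

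Rows two and six are the plain faults. Row three is a fault only where another item bounds the date, for example dead at 30 days.

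| Infection grade | Date of first infection | Class |
|---|---|---|
| II+ | day 10 | 1 |
| II+ | day 35 | 0 |
| II+ | missing | missing |
| all components none or I | – | 0 |

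The infection rule has a class for late events; the mortality rule has no counterpart.

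**2. Plan's own figure.** Section 4: 30% against 25%, 80% power, 5% type I error. Two proportions, pooled variance, two-sided, no continuity correction gives 1251 per arm, 2502 in total, as stated. This point does not change it.

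**3. Effect of undated infections.** Let p be the true risk in an arm and q the share of its in-window infections left undated and so excluded.

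- Observed risk = p(1−q)/(1−pq).
- Observed odds = p(1−q)/(1−p), so the odds ratio is multiplied by (1−q1)/(1−q0), with 1 the intervention arm and 0 usual care.
- Design odds ratio = (0.25/0.75)/(0.30/0.70) = 0.778.

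The values of q are assumptions; the SAP gives none.

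| q0 (usual care) | q1 (intervention) | Multiplier | Odds ratio, from 0.778 |
|---|---|---|---|
| 5% | 5% | 1 | 0.778 |
| 2% | 4% | 0.96/0.98 = 0.980 | 0.762 |
| 2% | 6% | 0.94/0.98 = 0.959 | 0.746 |
| 0% | 5% | 0.95 | 0.739 |
| 5% | 0% | 1/0.95 = 1.053 | 0.819 |

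With 5% lost in both arms the rates read 0.285/0.985 = 28.9% and 0.2375/0.9875 = 24.1%, and unadjusted power falls from 80.0% to 78.5%.

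**4. The 1% trigger.** 1% of 2502 is 25 patients. At a mean risk of 27.5% there are about 0.275 × 2502 = 688 infections, so 25/688 = 3.6% of them would have to be undated before this source alone triggers the MNAR analysis. Other missing data can trigger it sooner, and the undated infections are then imputed too. If 20 undated infections were among the missing in one arm, on average about 0.15 × 20 = 3 to 0.40 × 20 = 8 would be counted as infected in usual care, and 0.05 × 20 = 1 to 0.50 × 20 = 10 in the intervention arm.

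**5. Mortality, illustration only.** Assume 180-day mortality of 6% to 10%, 35% of deaths by day 30, and 20% of those with a blank 180-day item. None of these is in the SAP.

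- At 10%: 1251 × 0.10 × 0.35 × 0.20 = 8.76 deaths lost per arm; (125.1 − 8.76)/(1251 − 8.76) = 9.4%.
- At 6%: 1251 × 0.06 × 0.35 × 0.20 = 5.25 deaths lost per arm; (75.06 − 5.25)/(1251 − 5.25) = 5.6%.

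**The case against.** An undated infection or death is not known to lie inside its window. The SAP expects some infections after day 30 and codes them 0, so setting an undated one to missing reflects real uncertainty. This stands, and it is why the main rule for infection should not simply be reversed. The kidney injury and cardiac derivations ask for no separate date, but the items they use are already described as within the window, so the contrast is suggestive only.

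The blank-status fault bites only if a patient known to be dead has the 180-day field left empty. Data entry may carry earlier deaths forward, and the 30-day mortality variable may itself be derived from the date of death; only the discharge item is clearly a separate record. This also stands as a limit on size. But the SAP does not say that deaths are carried forward, and the rule as written has no exception.

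A death dated after day 180 is arguably 0 by the outcome's title. That is the sensible reading, but Appendix 1 exists to state it and does not.

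A reader might infer that these rules remove events only, and so bias the infection rate downwards. The SAP does not support that. The blank-status rule also drops survivors lost to follow-up. The infection rule also drops patients with a missing component when all other components are none or grade I, many of them probably non-events, while it keeps a patient with a dated grade II+ infection despite other gaps. The net direction is unknown.

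**Conclusion.** The point holds for the derivation rules as written. A blank 180-day status overrides a death recorded elsewhere, and deaths after day 180 have no class; both need correcting on any reading. Undated grade II+ infections may be missing in the main analysis, but they do not belong in a grid of 0.05 to 0.50, because the chance that they fell in the window is likely much higher.

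The size cannot be read from the document. The figures above rest on assumed shares of blank statuses and undated infections. It would be tempting to conclude that the odds ratios are biased; that follows only if the loss differs between arms. The trial is open, and Table 14 allows for assessors who knew the allocation, so equal completeness cannot be taken for granted, but nothing in the SAP shows that it differs. With equal loss the odds ratio is unchanged, and the cost is fewer counted events, lower reported rates and slightly less power.

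**What to change.** **Mortality.** Code 1 if any source (discharge item, 30-day mortality, 180-day status, date of death) places death by day 180, including an undated death that another item bounds within the window. Code 0 if the patient was alive at day 180 or the date of death is after day 180. Code missing only if vital status at day 180 cannot be determined from any source.

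**Undated grade II+ infections, and undated deaths that no other item bounds.** Keep the main rule, and add a sensitivity analysis that counts them as events.

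**MNAR analysis.** Do not draw undated grade II+ infections from the grid. Handle them separately, as events or with an event probability near 1, and apply the grid to the remaining missing outcomes.

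The cost is a few lines of SAP wording and derivation code, with no new data. The downside is that a few undated events counted in the sensitivity analyses may truly have fallen outside the window.
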